Study Title: Randomized, double blinded, placebo controlled trial comparing intrathecal morphine with placebo in patients undergoing robotic totally endoscopic beating heart coronary revascularization and intraoperative extubation (TECAB)

NCT #: 03241485

Protocol Version Date: 26JUN2019

PI: [name]. MD MPH

MATERIALS AND METHODS

This clinical trial was approved by the University of Chicago Institutional Review Board (IRB) and was registered at Clinicaltrials.gov (NCT03241485) on August 7, 2017 prior to patient enrollment. This manuscript conforms to the Consolidated Standards of Reporting Trials guidelines. The trial was conducted in adherence to the original protocol, which is available upon request. This randomized, placebo-controlled, double-blinded clinical trial was conducted at The University of Chicago Medical Center. Patients were screened for eligibility and informed consent obtained on day of surgery in the preoperative area by a member of the study team. Inclusion criteria were patients undergoing elective totally endoscopic CABG without anticipated cardiopulmonary bypass (CPB) support and with anticipated intraoperative extubation. Exclusion criteria included emergency surgery, anticipated CPB support, anticipated postoperative extubation, previous cardiothoracic surgery, left ventricular ejection fraction less than 40%, preoperative cardiac support (intravenous [IV] inotropes and/or vasoconstrictors/intraaortic balloon pump), severe pulmonary disease (home oxygen requirement and/or recent steroid use), renal dysfunction (serum creatinine greater than 1.5 mg/dL), hepatic impairment, preoperative opioid use and/or history of opioid abuse, morbid obesity (body-mass index greater than 35 kg/m²), and any contraindication to intrathecal injection (morphine allergy, coagulopathy, patient refusal). Selected exclusion criteria reflect patient characteristics that would not likely allow for immediate tracheal extubation and assessment of pain scores. The primary outcome is postoperative morphine equivalent consumption in the first 24 h after surgery. Secondary outcomes include postoperative pain scores, opioid-related side effects, and self-reported patient satisfaction.

Following written informed consent, patients were randomized to receive either intrathecal morphine (5 mcg/kg, Morphine Group) or intrathecal placebo (sterile saline, Placebo Group). Based on previous clinical trials, the dose of intrathecal morphine was selected to potentially facilitate postoperative analgesia without hindering immediate extubation.^{11,12}

Prior to study commencement, a study statistician created a computer generated randomization list (using simple randomization) to allocate study arm assignments in 1:1 ratio, which was provided to an operating room pharmacist who prepared the appropriate intrathecal solution. On the day of surgery, the principal investigator assessed the patient for eligibility, obtained informed consent, and enrolled the participant in the trial. After informed consent, the pharmacist, based on the sequentially numbered randomization list, prepared either a placebo or morphine syringe. Ultimately, a three ml syringe (total volume one ml clear solution) was delivered to the anesthesia caregiver. All syringes, regardless of saline or morphine solution, appeared identical. All caregivers were blinded to Group assignment throughout hospital stay.

Both Groups were treated identically during the preoperative/intraoperative period. Following application of standard American Society of Anesthesiologists monitors and achieving IV access, one mg IV midazolam was given and the patient assumed the sitting position. After normal prepping/draping and local infiltration with lidocaine, a 24-gauge Sprotte (Pajunk, Germany) needle was inserted via the L3-4 or L4-5 interspace (introducer-assisted) under sterile conditions. Upon free return of clear cerebrospinal fluid (CSF), the one ml study solution was injected and the Sprotte needle removed. The patient then assumed the supine position, a radial arterial line was inserted, and general anesthesia induced.

Intraoperative anesthetic technique was standardized in all patients. Induction consisted of IV midazolam (2-4 mg), sufentanil (0.5 mcg/kg), propofol (1 mg/kg), and rocuronium (0.6

mg/kg). Following intubation, inhaled desflurane was adjusted to maintain a Bispectral Index (BIS[®] system; Aspect Medical Systems, USA) value of 40-60 and a mean arterial blood pressure within 20% baseline value. Supplemental propofol and rocuronium were allowed throughout, consistent with the goal of intraoperative extubation. A single-lumen endotracheal tube (8.0) was used, through which either an Arndt Blocker (Cook Critical Care, Bloomington, IN) or EZBlocker (Teleflex Life Sciences Ltd., Athlone, Ireland) was inserted and positioned via fiberoptic guidance to facilitate one-lung ventilation when required. While on two-lung ventilation, mechanical ventilation parameters were standardized (tidal volume 5 ml/kg ideal body weight, respiratory rate appropriate for normocarbida, FiO₂ 100%, and positive end-expiratory pressure 5 cm H₂O). Post-induction, a 9 French double-lumen introducer was inserted via the right internal jugular vein and intraoperative transesophageal echocardiography was used throughout.

All patients underwent totally endoscopic CABG without CPB support, via standard robotic thoracic ports (Figure 1) and the Da Vinci[®] surgical system (Da Vinci, Intuitive Surgical, USA). The left and/or right internal thoracic artery served as conduits. Typically, IV heparin was administered (100-150 units/kg; activated clotting time goal 250 seconds) prior to distal anastomoses, which was ultimately reversed with IV protamine (1 mg/100 units heparin). All patients had thoracic port incisions injected with 0.25% bupivacaine (30 ml total divided volume) at the conclusion of surgery. Once surgery was finished, consultation between the attending surgeon and anesthesiologist determined timing of attempted extubation (intraoperative or immediately postoperative). If intraoperative extubation was attempted, IV sugammadex (2 mg/kg) and ondansetron (4 mg) were administered. IV ketorolac (15 mg) was allowed if emergence tachycardia/hypertension occurred. Extubation was accomplished once specific

criteria were met. IV fentanyl was allowed if clinically indicated (pain) prior to transport to the intensive care unit (ICU).

Postoperative care was standardized in all patients. Patients not undergoing intraoperative extubation were extubated at the earliest clinically appropriate time in the ICU once the same specific intraoperative extubation criteria were met. The dates of patient enrollment in the clinical trial were June 19, 2018 to August 31, 2020. Postoperative analgesic technique in the ICU consisted of IV fentanyl (25 mcg as needed) initially (June 19, 2018 to February 8, 2019), then transitioned to IV morphine (patient-controlled analgesia [PCA] pump: 2 mg dose, lockout interval 8 minutes) later (February 19, 2019 to August 31, 2020). The reason for this transition was the University of Chicago experienced an IV morphine drug shortage/unavailability during the initial period of the study. During the entire study period, IV fentanyl (25 mcg), IV ketorolac (15 mg every six h, maximum four doses) and/or IV hydromorphone was administered in the ICU, if needed. Once discharged to the surgical ward, all patients received oral hydrocodone-acetaminophen (5 mg-325 mg), oxycodone (5 mg), and/or tramadol (50 mg), if needed. Morphine equivalents were then calculated as previously described.¹³ Equivalent doses to 1.0 mg IV morphine and conversion factors used for specific drugs were IV fentanyl (0.01 mg/0.10), IV hydromorphone (0.15 mg/6.70), oral hydrocodone (3.0 mg/0.30), oral oxycodone (2.0 mg/0.50), and oral tramadol (15 mg/0.06).

Data Collection

Data was collected by research team members and nurses who were blinded to Group assignment. Preoperative data was collected from electronic medical records. Postoperatively, a data collection sheet was given to ICU/surgical ward nurses to capture secondary outcomes. In addition, patient electronic medical records were accessed for verification. Pain was evaluated in the ICU and surgical ward per nurse at 1, 2, 6, 12, 24, and 48 h following ICU admission via a visual analog scoring (VAS) system (0 to 10 scale, 0 = no pain, 10 = worst pain imaginable) at rest and with cough.

Opioid-related side effects (nausea/vomiting, pruritus, urinary retention, and respiratory depression) were evaluated in all patients daily by nurses until hospital discharge. Patients were questioned regarding occurrence of nausea/vomiting and pruritus. Urinary retention was defined as need for reinsertion of a urinary catheter or straight catheterization after Foley catheter removal. Opioid-specific respiratory depression was defined as prolonged tracheal re-intubation secondary to hypercarbia (arterial blood gas analysis) and/or escalation of respiratory support following extubation thought to be secondary to hypercarbia.

Prior to hospital discharge, patients completed the Revised American Pain Society Outcome Questionnaire, which evaluates subjective experiences of pain following surgery.¹⁴

Power Analysis/IRB Termination

Recent clinical research indicates that when comparing two different intraoperative anesthetic techniques in patients undergoing cardiac surgery, a reduction in postoperative morphine requirements during the initial 24 h from a median of 10 mg to 6 mg was observed.¹⁵ With a

one-sided significance level of 0.05 and anticipated 5 mg mean difference (standard deviation of 8 mg), calculated power was 96% for 120 patients total (60 per Group). Initial IRB approval was for study inclusion of 120 patients (60 per Group).

Interim analysis of data for presentation in abstract form yielded statistically significant differences between the two Groups regarding primary and secondary outcomes. Thus, on 9/21/2020 the IRB chose to permanently close the study for enrollment because “the primary end point of this study had been met with statistical significance with fewer number of subjects than what was originally planned”.

Statistical Analysis

Variables were summarized as mean \pm SD for normally distributed continuous variables, median (25th-75th percentile) for continuous variables with evidence of non-normality or for ordinal variables, and frequency counts and percentages for categorical variables. For the primary outcome (amount of postoperative morphine use) and secondary outcomes (i.e. pain scores, patient satisfaction), comparisons between the treatment Groups were performed using the Wilcoxon rank-sum test (otherwise known as the Mann-Whitney U test). For side effects (secondary outcomes) and other categorical variables, comparisons were made using the chisquared test. However, if there was an expected cell count of <5 , then Fisher’s exact test was utilized.

For pain medication and pain score data, differences between treatment Groups were calculated along with 95% confidence intervals (CIs) using the cendif command in Stata, based on the Hodges-Lehmann method and consideration of all pairwise differences between the two

sets of observations. In addition, box plots were generated for pain scores, stratified by treatment Group and time. As a sensitivity analysis, and to obtain an overall estimate of treatment effect on pain, mixed-effects models were fit (Appendix 2).

Statistical significance was defined as a two-tailed $p < 0.05$ based on tests of superiority; no formal adjustment for multiple testing or interim looks was made. Statistical analyses were performed using Stata 16 (StataCorp LLC, College Station, TX).

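### The printed conversion factor for oral hydrocodone is 10% below the reciprocal of its printed equivalent dose; tramadol shows the same gap, which may be only rounding

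*Combined protocol and SAP*

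**What the plan says.** The primary outcome is defined in Materials and Methods: "The primary outcome is postoperative morphine equivalent consumption in the first 24 h after surgery". The postoperative-care text in the same section says how different opioids are put on one scale. It refers to a cited source ("Morphine equivalents were then calculated as previously described") and then prints two figures per drug, introduced as "Equivalent doses to 1.0 mg IV morphine and conversion factors used for specific drugs". The three oral drugs read "oral hydrocodone (3.0 mg/0.30), oral oxycodone (2.0 mg/0.50), and oral tramadol (15 mg/0.06". The two IV drugs are fentanyl, 0.01 mg with factor 0.10, and hydromorphone, 0.15 mg with factor 6.70. No rounding rule is given, and no unit is attached to any factor.

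The oral drugs belong to ward care after discharge from the ICU: "oral hydrocodone-acetaminophen (5 mg-325 mg), oxycodone (5 mg), and/or tramadol (50 mg), if needed". The time of transfer to the ward is not stated.

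Under Statistical Analysis, the primary outcome is tested as follows: "comparisons between the treatment Groups were performed using the Wilcoxon rank-sum test". Group differences in pain medication are estimated "using the cendif command in Stata, based on the Hodges-Lehmann method".

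**The concern.** The two figures in each pair express one fact. If x mg of a drug equals 1.0 mg IV morphine, then 1 mg of it equals 1/x mg, and the factor must be 1/x. For hydrocodone and tramadol the printed factor is lower than 1/x by a tenth. A reader who computes the outcome from the dose column therefore gets a different 24 h total from one who uses the factor column.

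What is at stake is the definition of the primary endpoint. If the factors were applied and the printed doses are the correct ones, every counted dose of the affected drug was credited 10% too little. If the factors are the correct ones, the text misstates the equivalence and the totals are unaffected. The Hodges-Lehmann difference is in mg, so it could move even where the rank test does not.

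**Working it through.** **Inputs.** All doses d and factors f come from the postoperative-care text in Materials and Methods. With matching units, f × d should equal 1.

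**Rounding check.** Each printed figure is taken as accurate to half a unit in its last printed digit. The dose range implied by the factor is 1/(f + 0.005) to 1/(f − 0.005).

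| Drug | d | f | 1/d | f × d | Range of d as printed | Range of d implied by f | Do they meet? |
|---|---|---|---|---|---|---|---|
| Fentanyl, read as mcg | 10 mcg | 0.10 | 0.100 | 1.000 | 5 to 15 mcg | 9.52 to 10.53 mcg | yes |
| Hydromorphone | 0.15 mg | 6.70 | 6.667 | 1.005 | 0.145 to 0.155 mg | 0.1491 to 0.1494 mg | yes |
| Oxycodone | 2.0 mg | 0.50 | 0.500 | 1.000 | 1.95 to 2.05 mg | 1.980 to 2.020 mg | yes |
| Hydrocodone | 3.0 mg | 0.30 | 0.333 | 0.900 | 2.95 to 3.05 mg | 3.279 to 3.390 mg | no |
| Tramadol | 15 mg | 0.06 | 0.0667 | 0.900 | 14.5 to 15.5 mg | 15.38 to 18.18 mg | only 15.38 to 15.5 mg |

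Oxycodone reproduces exactly and hydromorphone to 0.5%. Fentanyl does not reproduce in the unit printed, since 1/0.01 = 100 per mg. It reproduces exactly per mcg, since 1/10 = 0.10.

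**Coarser rounding rules.**
- Two decimals gives 0.33 and 0.07, so it fits neither hydrocodone nor tramadol. It also gives 6.67 for hydromorphone, where 6.70 is printed.
- One decimal with a zero added gives 0.30 for hydrocodone and 6.70 for hydromorphone, both as printed, but 0.1 for tramadol.
- Truncation to two decimals gives 0.06 for tramadol, as printed, but 0.33 for hydrocodone.

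None of these rules gives all five printed factors. One-decimal rounding is a plausible origin for 0.30, but a factor rounded that far still credits 10% less than the dose printed beside it.

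**Size per dose**, dose column against factor column:
- Hydrocodone 5 mg: 5/3.0 = 1.67 mg against 5 × 0.30 = 1.50 mg; gap 0.17 mg.
- Tramadol 50 mg: 50/15 = 3.33 mg against 50 × 0.06 = 3.00 mg; gap 0.33 mg.

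For scale, one PCA dose is 2 mg ("pump: 2 mg dose, lockout interval 8 minutes"). The gap adds up to that after 2/(1/6) = 12 hydrocodone doses or 2/(1/3) = 6 tramadol doses.

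**Size between arms.** Switching columns shifts the difference in means by the gap times the difference in mean number of 24 h doses. A 1 mg shift needs the arms to differ by 1/(1/6) = 6 hydrocodone doses or 1/(1/3) = 3 tramadol doses per patient. The difference anticipated under Power Analysis/IRB Termination is 5 mg, with SD 8 mg. The rank-sum result changes only where two patients swap order, or become tied or untied. For that, their totals must lie within 0.17 mg per extra hydrocodone dose or 0.33 mg per extra tramadol dose.

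**Illustration under assumptions, not trial data.** The assumptions are:
- IV totals are gamma, with means 15 mg (placebo) and 10 mg (morphine), SD 8 mg, in 2 mg steps.
- Ward doses of one drug within 24 h are Poisson, with mean 1 in the morphine arm and 1, 1.5 or 2 in the placebo arm.
- Each scenario has 1,000 trials.

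Switching columns changed whether two-sided p < 0.05 in at most about 2% of trials at 30 per group and 0.6% at the planned 60. The mean Hodges-Lehmann shift (dose column minus factor column) was about 0 to 0.17 mg for hydrocodone and 0 to 0.34 mg for tramadol. In single trials the central 95% of shifts was at most −0.33 to 0.50 mg and −0.67 to 1.0 mg respectively. All scenarios place ward doses inside the 24 h window, which the documents do not establish.

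**The case against.** The strongest reply is that nothing needs recomputing. The introductory wording indicates that the factors are what was applied, so the factor column is the working definition and the dose column may be only descriptive. The same factors serve both arms, the test is rank-based, and the gaps are small against 5 mg. Most of this stands. It makes the outcome computable and limits the matter to a minor correction. It does not remove the contradiction, because a factor of 0.30 still differs by 10% from the equivalence stated beside it, and the documents do not show which figure matches the cited source.

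Three further limits also stand. First, a reader might infer that tramadol is a second proven error. It is not: a true dose of 15.38 to 15.5 mg, or truncation of 0.0667, would give 0.06. Only hydrocodone is a firm mismatch at the printed precision.

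Second, a reader might infer that 24 h consumption was under-counted and the group comparison distorted. The documents do not support that. The oral drugs were given as needed after ward transfer, at an unstated time, and if none was given within 24 h the effect is exactly zero.

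Third, a reader might take the fentanyl pair as a thousandfold error. Read per mg, the factor would turn a 25 mcg dose into 0.025 × 0.10 = 0.0025 mg. Read per mcg, it gives 25 × 0.10 = 2.5 mg, the same as the dose column (0.025/0.01 = 2.5). Since the plan states fentanyl doses in mcg, a missing unit label is the likelier explanation.

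**Conclusion.** The point holds as a minor correction to the definition of the primary outcome. The hydrocodone pair contradicts itself by 10%. The tramadol pair shows the same gap but may be only rounding or truncation. The fentanyl pair lacks a unit. This rests on reading each pair as a dose and its reciprocal, which the oxycodone and hydromorphone pairs bear out.

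The effect on the primary comparison is probably small. It cannot be determined, because 24 h use of the two drugs is not given. If the factors were applied and the printed doses are right, the direction would depend on which arm took more of these drugs: more use in the placebo arm would make the reported difference slightly too small, and more use in the morphine arm slightly too large. Nothing here is a reason to doubt the trial's conclusion.

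**What to change.** Check the hydrocodone and tramadol pairs against the cited conversion source and correct whichever column is wrong. Print the tramadol factor to enough digits to be checked, state the unit of every factor (per mg or per mcg, including fentanyl), and state that these factors define the 24 h outcome.

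Only if the factors actually applied differ from the corrected ones, recompute the 24 h totals and re-run the Wilcoxon test and the Hodges-Lehmann difference with its confidence interval.

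The cost is a corrected sentence and, in the second case only, one derived variable and one comparison.

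### Respiratory depression is counted only through hypercarbia-attributed re-intubation or support escalation, so an episode treated with an opioid antagonist alone scores as no event

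*Combined protocol and SAP*

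**What the plan says.** Materials and Methods gives the outcome its rank: "Secondary outcomes include postoperative pain scores, opioid-related side effects, and self-reported patient satisfaction". The comparison is a neuraxial opioid against saline: "patients were randomized to receive either intrathecal morphine (5 mcg/kg, Morphine Group) or intrathecal placebo (sterile saline, Placebo Group").

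Data Collection contains the only definition of respiratory depression: "Opioid-specific respiratory depression was defined as prolonged tracheal re-intubation secondary to hypercarbia (arterial blood gas analysis) and/or escalation of respiratory support following extubation", and the sentence ends "thought to be secondary to hypercarbia". It has two routes joined by *and/or*:

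- Route 1: a prolonged re-intubation caused by hypercarbia, with blood-gas analysis.
- Route 2: "escalation of respiratory support following extubation thought to be secondary to hypercarbia".

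The same section says that the four listed side effects "were evaluated in all patients daily by nurses until hospital discharge". Only two of them are put to the patient directly: "Patients were questioned regarding occurrence of nausea/vomiting and pruritus". Statistical Analysis compares side effects between Groups by the chi-squared test, or by Fisher's exact test when an expected count is below 5.

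**The concern.** Both routes require two things: an intervention on the airway or on respiratory support, and attribution of the problem to hypercarbia. An extubated patient with a slow respiratory rate and deep sedation who is given an opioid antagonist and recovers without added support meets neither route. This is a recognisable opioid effect, and the outcome has no place for it.

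Route 2 has a second weakness. Blood-gas analysis is attached to route 1 only. Route 2 rests on what someone thought the cause was, with no PaCO2 value, so two assessors could score the same escalation differently.

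What is at stake is the safety statement. The trial adds intrathecal morphine to intraoperative sufentanil and to postoperative intravenous opioids. If few or no events are recorded in either arm, it is easy to write that intrathecal morphine caused no respiratory depression. The definition supports only a narrower statement.

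**Working it through.** **Step 1. Inputs.** The definition, its place among the secondary outcomes and the daily assessment come from the documents, as cited above. The planned 60 per Group comes from Power Analysis/IRB Termination. The documents give no respiratory event rate, and nothing on what fraction of episodes the definition would capture.

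**Step 2. The plan's own figure.** There is none for this outcome. The only design figure is 96% power for morphine consumption. It reproduces: 5 / (8 × √(2/60)) = 3.423; 3.423 − 1.645 = 1.778; Φ(1.778) = 0.962, one-sided. It says nothing about respiratory events.

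**Step 3. Cases set against the definition.** These cases are hypothetical.

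| Episode after extubation | Route 1 | Route 2 | Scored |
|---|---|---|---|
| Prolonged re-intubation, hypercarbia on blood gas | yes | yes | event |
| Short re-intubation for hypercarbia | no | yes, since re-intubation is itself an escalation | event |
| Noticed from slow rate or sedation; support raised for presumed hypercarbia | no | yes | event |
| Support raised for a cause identified as atelectasis | no | no | no event |
| Slow rate and sedation; antagonist given, no added support | no | no | **no event** |

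The last row is the gap.

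**Step 4. Does anything else in the documents catch the last row?** No. Sedation level, oxygen saturation and opioid-antagonist use are not named as criteria or as collected items. Respiratory rate appears once, as an intraoperative ventilator setting. Pain has six scheduled assessments (1, 2, 6, 12, 24 and 48 h after ICU admission), whereas side effects are assessed daily with no respiratory observation specified. The nurses' data collection sheet is not reproduced, so its items are unknown.

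**Step 5. Illustration of size, with assumed rates and capture.** The probability of recording no event in a Group of 60 is (1 − rate × capture)^60.

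| Assumed true rate | All captured | Half captured | A quarter captured |
|---|---|---|---|
| 5% | 0.95^60 = 0.046 | 0.975^60 = 0.219 | 0.9875^60 = 0.470 |
| 8% | 0.92^60 = 0.007 | 0.96^60 = 0.086 | 0.98^60 = 0.298 |
| 10% | 0.90^60 = 0.002 | 0.95^60 = 0.046 | 0.975^60 = 0.219 |

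The between-Group comparison weakens in the same way. Power below is for a two-sided Fisher test at 0.05 with 60 per Group, multiplying both rates by the capture fraction:

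| Assumed true rates, morphine v placebo | All captured | Half captured | A quarter captured |
|---|---|---|---|
| 10% v 2% | 28% | 5% | 0.3% |
| 20% v 5% | 63% | 23% | 4% |

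Equal capture in both arms leaves the ratio unchanged and shrinks the difference. At half capture, 10% v 2% becomes 5% v 1%: the ratio stays at 5 and the difference falls from 8 to 4 percentage points.

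Enrolment closed below the planned number. With fewer than 60 per Group, every probability in the first table would be higher.

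**The case against.** The strongest defence is that requiring an intervention is a legitimate choice. It selects events of clinical consequence, and it matches the urinary retention definition, which also needs an intervention (catheterisation). The definition is identical in both arms, caregivers and data collectors were blinded, and the outcome is one of four side effects within a secondary outcome. All of this stands. It is why the definition should be kept and why no directional bias is claimed. It does not close the gap, because the outcome's name is broader than what it counts.

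Several stronger readings are tempting, and the documents do not support them:

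- *Short re-intubations are missed.* Route 1 does require a prolonged re-intubation and gives no duration, but route 2 covers a re-intubation of any length. The word affects which route records the event, not whether it counts.
- *Episodes first noticed from rate or sedation are excluded.* They count if support was raised and hypercarbia was thought responsible. The exclusion is of episodes managed without re-intubation or added support, or not attributed to hypercarbia.
- *Escalation for atelectasis contaminates the count.* A cause identified as atelectasis fails route 2 on its face. What remains is a blinded judgement without a blood-gas anchor.
- *This is the main safety outcome.* The documents do not rank it so.
- *Events were miscounted.* The antagonist case is a constructed example. Nothing in the documents says that one occurred.

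It is also fair to object that the rates and capture fractions are not sourced. The tables show how a zero count behaves under under-capture; they do not show that this definition misses half or three-quarters of episodes.

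**Conclusion.** The point holds as a limited one about a secondary safety outcome. On the text alone, an opioid episode treated with an antagonist and without added support is scored as no event, and a route 2 event needs no blood-gas confirmation. A low or zero count in both arms would therefore speak only to hypercarbia-attributed episodes that led to re-intubation or escalated support. It would not show that intrathecal morphine caused no respiratory depression.

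The size cannot be fixed from the documents. Under the assumed true rates of 5% to 10% and half capture, the chance of a zero count among 60 morphine patients is between 5% and 22%, against 0.2% to 5% with full capture. These figures assume independent patients, the planned Group size and a constant capture fraction. The primary outcome and its analysis are untouched.

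**What to change.** 1. Keep the present definition and the follow-up until discharge. Label the outcome *hypercarbia-attributed respiratory depression requiring re-intubation or support escalation*.
2. Add a labelled supplementary outcome: any opioid-antagonist administration after extubation for sedation or breathing, extracted from the electronic records by staff blind to Group.
3. For each route 2 event, report whether a blood gas confirmed hypercarbia.
4. Show every component by arm, and limit the safety conclusion to what was captured.

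This changes how outcomes are counted and reported, not how patients are treated.

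Four wider changes are not worth making. Deleting the word *prolonged* would alter no count. A bare oxygen-saturation threshold would admit desaturation from atelectasis. Counting any re-intubation would lose the opioid-specific intent. A 24 h window from the intrathecal injection would begin before induction and drop events between its end and discharge.

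The cost is modest chart extraction. Data Collection says that electronic records were accessed for verification, which makes this plausible, but it does not confirm that antagonist use can be retrieved for every patient. Because enrolment has closed, the added component is post hoc and must be labelled so.

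### Does the respiratory-depression definition miss delayed first extubation, so that the plan needs an extubation outcome?

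*Combined protocol and SAP*

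**What the plan says.** The definition is in Data Collection and has two limbs. The first reads "Opioid-specific respiratory depression was defined as prolonged tracheal re-intubation secondary to hypercarbia", with hypercarbia established by arterial blood gas. The second, joined by *and/or*, is "escalation of respiratory support following extubation thought to be secondary to hypercarbia".

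The outcomes are named in Materials and Methods. The primary outcome is morphine-equivalent consumption over 24 h, and then "Secondary outcomes include postoperative pain scores, opioid-related side effects, and self-reported patient satisfaction". Data Collection lists four side effects: nausea/vomiting, pruritus, urinary retention and respiratory depression. Extubation status and time to extubation are in neither list.

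Extubation nevertheless runs through Materials and Methods. On eligibility: "Selected exclusion criteria reflect patient characteristics that would not likely allow for immediate tracheal extubation and assessment of pain scores". On the study drug: "the dose of intrathecal morphine was selected to potentially facilitate postoperative analgesia without hindering immediate extubation". At the end of surgery, "consultation between the attending surgeon and anesthesiologist determined timing of attempted extubation (intraoperative or immediately postoperative". For the rest, "Patients not undergoing intraoperative extubation were extubated at the earliest clinically appropriate time in the ICU", under the same criteria as in the operating room.

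Statistical Analysis covers categorical data in general terms: "For side effects (secondary outcomes) and other categorical variables, comparisons were made using the chisquared test", with Fisher's exact test when an expected count is below 5.

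**The concern.** The study drug is given before induction and the timing of extubation is decided after surgery. Extubation is therefore a post-randomization event that the drug could affect. If intrathecal morphine delayed the first extubation through hypercarbia, the literal definition would not record it unless a further event followed, and no other named outcome would show it. A low count of respiratory depression could then be taken to cover the whole period from injection when it covers only the period after extubation. The plan would also have no named comparison to test its own reason for the dose. What is at stake is the completeness of the respiratory safety picture; the estimate of opioid consumption is not affected.

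**Working it through.** **What the definition counts.** Two readings of the first limb are possible.

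| Patient | Literal reading | Reading that includes prolonged initial intubation |
|---|---|---|
| Extubated, later re-intubated for hypercarbia | counted | counted |
| Extubated, support escalated for presumed hypercarbia | counted | counted |
| First extubation delayed by hypercarbia, no later event | not counted | counted |
| First extubation delayed for another reason | not counted | not counted |

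The readings differ only in the third row. The word *prolonged* sits more naturally with intubation that continues than with a new one, so a slip for prolonged intubation and/or re-intubation is plausible. The text does not settle it. Under the second reading the gap in the definition closes.

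**Whether extubation is left out of the analysis.** The secondary outcomes are introduced by *include*, which does not close the list. Intraoperative extubation (yes/no) is a categorical variable and falls under the general chi-squared/Fisher provision. Time to extubation is continuous: it would be summarized under the general rule, but no test is named for it. So extubation is unnamed, which is not the same as excluded.

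**What a by-arm comparison could show.** The plan's only sample-size figure concerns the primary outcome. It reproduces: 5 / (8 × √(2/60)) = 3.423; 3.423 − 1.645 = 1.778; Φ(1.778) = 96.2%, against the stated 96%. It does not bear on this point except to supply 60 per arm. The documents give no rate of delayed extubation and no final arm size, so the rates below and the 40 per arm are assumptions.

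Newcombe interval for a difference d = p₁ − p₂, with Wilson limits (l, u) for each arm:
- lower = d − √[(p₁ − l₁)² + (u₂ − p₂)²]
- upper = d + √[(u₁ − p₁)² + (p₂ − l₂)²]

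For 12/60 against 6/60, the Wilson limits are 11.83 to 31.78% and 4.66 to 20.15%:
- lower = 10 − √(8.17² + 10.15²) = 10 − 13.03 = −3.0 points
- upper = 10 + √(11.78² + 5.34²) = 10 + 12.93 = 22.9 points

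| Assumed rates | 60 per arm | 40 per arm |
|---|---|---|
| 20% vs 10%: difference 10 points, 95% CI | −3.0 to 22.9 | −6.1 to 25.9 |
| 10% vs 10%: difference 0, 95% CI | ±11.5 | ±14.4 |
| Fisher power, 20% vs 10%, two-sided 0.05 | 24.7% | 16.2% |
| Rate giving 80% Fisher power against 10% (0.5-point grid) | 32.0% | 38.0% |

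These figures apply to the yes/no comparison only. No power was worked out for time to extubation, and none can be without an assumed distribution.

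**Whether the primary result is affected.** Morphine equivalents over 24 h are compared by Wilcoxon rank-sum. Neither the outcome nor the test uses the respiratory-depression definition.

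**The case for a change.** The best case for a change is that extubation is central here: it is in the title, the eligibility rules and the reason for the dose. Comparing it by arm would cost one or two tests of kinds the plan already uses, and needs no new patients if extubation times are in the records. The two readings count different patients, and a reader cannot tell which was used. The generic provision for categorical variables does not reach time to extubation, and confidence intervals are stated only for pain medication and pain scores.

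Much of this is right on the facts. The wording is ambiguous and no extubation outcome is named. It does not show that following the plan gives a wrong answer. The second limb says openly that it concerns events after extubation, so a reader who takes the count to cover the whole period has passed over the definition. Every patient also receives sufentanil, midazolam and desflurane, and the timing of the attempt is a joint clinical judgment, so delay is a poor marker of an effect specific to the study drug. Caregivers are blinded and the extubation criteria are common to both arms. An added comparison would be post hoc unless already specified elsewhere, and a difference would not by itself point to hypercarbia. The missing intervals concern how all side effects are reported, which is a separate matter.

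**Conclusion.** The concern is accurate as a reading of the text, but it does not call for a change. What remains is an unclear phrase and an unnamed descriptive variable. Analysts would ordinarily fill both when reporting, by saying which reading was used and by tabulating extubation by arm with the other perioperative data. The respiratory-depression result is sound for what it defines, and the primary analysis does not depend on it.

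The size of any missed effect cannot be computed, because the documents report neither delayed extubations nor respiratory events. At the assumed 20% and 10%, a formal yes/no comparison would have about 25% power at the planned 60 per arm and 16% at an assumed 40, so a null result could not be read as absence of delay. This conclusion rests on taking the open outcome list and the general categorical provision at face value, and on accepting that an opioid-specific endpoint may leave out delay with several possible causes.
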